- 1. Protocol Title:** Paravertebral Block Versus Pectoral Nerve Block for Analgesia Following Mastectomy
- 2. Investigator(s):** [name] MD, [name], [name], [name], [name], [name], [name] and [name]
- 3. Version Date:** March 30, 2018
- 4. Objectives:**
 - I. Primary Objective: To determine if pectoral nerve blocks (PECs) achieve equal analgesia following mastectomy, partial mastectomy or lumpectomy, with and without reconstruction, when compared to paravertebral blocks (PVBs).
 - II. Secondary Objective: To trend complication rates for PECs and PVBs.

5. Background:

Postoperative pain control is essential following any major operative procedure. A variety of methods have been utilized to ensure adequate analgesia, each with its own advantages and risks. Increasingly, attention has focused on regional methods of analgesia, which may allow for reduction in systemic narcotic use and their associated complications [1]. Proposed benefits of regional analgesia and a resultant reduction in narcotic use include decreased risk of cancer progression, decreased length of stay, and decreased risk of ileus.

The most common regional block used to achieve postoperative analgesia following mastectomy is the paravertebral block, during which local anesthetic is injected into the paravertebral space which contains the thoracic spinal nerves, between the costotransverse ligament and the pleura. At our institution there has been recent interest in an alternative regional block. The pectoral nerve block is performed by injecting anesthetic between the pectoralis major and the pectoralis minor (PECs I) or between the pectoralis minor and the serratus anterior (PECs II) [2]. A serratus plane block is a modification of the PEC block, in which a local anesthetic is injected between the serratus anterior and latissimus dorsi muscles.

The proposed advantage of the pectoral nerve block for regional anesthesia during breast surgery is equal analgesic efficacy with fewer potential complications.

6. Setting of the Research:

The study will take place at Spectrum Health Medical Center: Butterworth Hospital and Spectrum Health Blodgett Hospital with follow up through Spectrum Health Lemmen-Holton Cancer Pavilion and the Lake Drive locations.

7. Resources Available to Conduct this Research:

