Length of operation, estimated blood loss, incidence of postoperative nausea, subjective pain at two weeks (including patient's overall pain rating for the previous two weeks, the patient's stated last time they used pain pills) and number of calls to physician's office following hospital discharge.

d. Procedures Involved in the Research

This is a prospective, randomized study.

Following satisfaction of the inclusion/exclusion criteria and signed informed consent, patients will be randomized to paravertebral block or a pectoral nerve block. The randomization schedule will be set-up prior to study start using an Excel spreadsheet. Spectrum Health statisticians designed the randomization schedule to meet significance for the endpoints. Randomization is 1:1, PEC:PVB. If the patient is unwilling to be randomized to one or the other type of block, they will not be able to participate in the study. After each patient is consented, the randomization schedule will be checked and the data sheet with the type of block to be used will be placed in

the patient chart. The research coordinator will notify anesthesia of which block will be used on the patient.

Patients will proceed to surgery per usual standard of care. The PVB is performed along the spine utilizing ultrasound guided technique. The PEC is performed anteriorly, at the level of the axillary line, also utilizing ultrasound guided technique. Each block will be performed using 20-30 mL 0.5% Ropivacaine¹ per side. Midazolam and fentanyl will be used for sedation as needed. Intraoperatively, patients will undergo monitored anesthesia care with a propofol infusion (50-150 mcg/kg/min). Additional IV fentanyl will be given as needed. Anesthesia will be converted to general anesthesia if the patient is unable to tolerate the procedure with sedation and block anesthetic or if general anesthesia is preferred by the surgeon. This will not disqualify the patient, but the conversion will be noted in REDCap.

¹Package inserts for these FDA-approved drugs are included as Appendix A to the protocol.

All post-operative care will be standard of care.

Data collected will include the following:

- i. Demographics¹
- ii. Medical history²
- iii. Surgical procedure performed & pain control technique(s) used
- iv. Extra doses of narcotic and sedative medication used during surgery.³
- v. Length of surgery
- vi. Duration of hospital stay (measured in minutes)

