Data to be collected are detailed in Appendix B (pdfs of REDCap database for this study). Data will be managed by Spectrum Health research staff and kept in a locked cabinet or a limited-access electronic drive.

f. Provisions to Monitor the Data for the Safety of Subjects

The Principal Investigator will oversee the safety of the study. This safety monitoring will include careful assessment and appropriate reporting of adverse events (see "Adverse Events" below).

g. Withdrawal of Subjects

A patient may be withdrawn from the study prior to the expected completion of that subject for failure to adhere to protocol requirements. Patients may choose to withdraw from the study at any time. Data that have already been collected on these patients will still be used.

The primary investigator may remove a patient at any time from this research study if it is felt to be in the best interest of the patient.

9. Statistical Plan:

a. Sample Size Determination

The primary outcome variable for this study is the difference in narcotic use between the PEC group and the PVB group during the first 24 hours following surgery. If we define a clinically important effect as the mean narcotic use in the PVB group is twice that seen for the PEC group, with a standard deviation equal to the mean of the PVB group, with $\alpha=0.05$ and $\beta=0.20$, we will be able to detect a statistically significant difference with 64 subjects in each group, using the unpaired t-test. Complication rates will also be compared between the two

groups, although with an anticipated rate of only 5% in the PVB group, it is unlikely with the projected sample size that we will find a statistically significant effect for this variable.

b. Statistical Methods

Summary statistics will be calculated. Quantitative data will be expressed as the mean + SD, while nominal data will be expressed as a percentage. Comparisons between groups for quantitative variables will be performed using the t-test. Nominal variables will be evaluated using the Chi-Square test. The data will be analyzed as intention to treat. Significance will be assessed at $p<0.05$.

10. Risks to Subjects:

Risks of both procedures are very low – less than 5% for each risk listed here.

PEC

- a. Vascular puncture
- b. Inadequate analgesia
- c. Intraneuronal injection, resulting in transient neuropathy
- d. Incomplete nerve block
- e. Infection

PVB

- a. Pneumothorax
- b. Vascular puncture
- c. Incomplete nerve block

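### Complications are to be compared only by assigned block; a table by block actually received should stand beside that comparison

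*Combined protocol and SAP*

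**What the plan says.** The secondary objective in Section 4 is "To trend complication rates for PECs and PVBs", so it is worded by procedure. Section 9a adds "Complication rates will also be compared between the two" groups, "with an anticipated rate of only 5% in the PVB group", and concedes that a significant result is unlikely at the planned size. It does not say whether the groups are formed by assignment or by block received.

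Section 9b settles that with one sentence covering all outcomes: "The data will be analyzed as intention to treat". The test for complications is the general one: "Nominal variables will be evaluated using the Chi-Square test". No safety population, as-treated table or exception for adverse events appears anywhere. Nor is there a rule for a patient who receives the other block, both blocks or neither.

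The block given is captured. Under Procedures Involved in the Research, data item iii is "Surgical procedure performed & pain control technique(s) used", and footnote 2 to the Schedule of Events also lists the block procedure used.

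Section 10 lists risks separately for each block. Pneumothorax, and hypotension from intrathecal or epidural spread, appear only under PVB. Yet the Adverse Events text of the same section names pneumothorax and hypotension as potential side effects of PEC.

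**The concern.** A procedural harm follows from the block that was performed. If a patient assigned to PEC is given a PVB and then has a complication of it, intention to treat records that event in the PEC arm. A patient who receives no block stays in her arm's denominator without having been exposed. Neither is an error in a comparison of assigned strategies, but neither gives the complication rate of a block, which is what the objective asks for.

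The Background and Section 11 present fewer complications as the possible advantage of PEC. Since significance is not expected, the reported counts are in effect the safety result. Those counts will be small, so how each event is attributed matters. Switching between blocks also has a known direction: it draws the two rates together and so would understate any real advantage of PEC.

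**Working it through.** **Inputs from the documents.** 64 patients per arm, 1:1 allocation; anticipated PVB complication rate 5%; chi-square test; significance level 0.05, power 0.80.

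**Inputs assumed, because the documents give neither.** PEC complication rate of 0%, 1% or 2.5%; share c of each arm receiving the other block, 0% to 20%, unrelated to complication risk.

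**1. The plan's own figure.** Section 9a sets "the mean narcotic use in the PVB group is twice that seen for the PEC group", with the SD equal to the PVB mean M. The standardized effect is (M − M/2)/M = 0.5. The normal approximation, two-sided, gives 2 × (1.960 + 0.842)² / 0.5² = 62.8, or 63 per arm. The exact t-test gives 63.8, so 64, with 80.1% power. The stated 64 is reproduced, and nothing below changes it.

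**2. Expected events.** 64 × 0.05 = 3.2 in the PVB arm. One event is 1/3.2, or about a third of that count.

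**3. Effect of switching on the assigned-arm rates.** With true rates v (PVB) and p (PEC):

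- PVB arm: (1 − c)v + cp
- PEC arm: (1 − c)p + cv
- difference: (1 − 2c)(v − p)

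Example with p = 1% and c = 10%: PVB arm 0.9 × 5% + 0.1 × 1% = 4.6%; PEC arm 0.9 × 1% + 0.1 × 5% = 1.4%; difference 3.2 points against a true 4.0.

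Reported difference in percentage points:

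| Assumed PEC rate | c = 0% | 5% | 10% | 20% |
|---|---|---|---|---|
| 0% | 5.0 | 4.5 | 4.0 | 3.0 |
| 1% | 4.0 | 3.6 | 3.2 | 2.4 |
| 2.5% | 2.5 | 2.25 | 2.0 | 1.5 |

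If only PEC patients switch, the factor is (1 − c): at p = 1% and c = 10%, 0.9 × 4.0 = 3.6 points. Patients given both blocks or none are outside this formula, and the direction of their effect depends on the arm they come from.

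**4. Expected misplaced events.** PVB complications counted under PEC are 64 × c × 0.05: 0.06 at c = 2%, 0.16 at 5%, 0.32 at 10% and 0.64 at 20%.

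**5. Power of the complication comparison.** Exact enumeration of the chi-square test without continuity correction, 64 per arm, 5% in PVB:

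| Assumed PEC rate | No switching | 10% symmetric switching |
|---|---|---|
| 0% | 40% | 24% |
| 1% | 22% | 15% |
| 2.5% | 10% | 8% |

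Power is low throughout, as Section 9a already says.

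**The case against.** The effect needs patients to receive a block they were not assigned, and the documents describe no such switching. Patients unwilling to accept either block cannot take part, randomization is on the day of surgery, and the coordinator tells anesthesia which block to use. The one departure provided for is conversion to general anesthesia, which is not a change of block. This stands in part. Switching is not excluded either: both blocks are standard of care, incomplete block is a listed risk of each, and no rule covers the case. Its frequency is simply unknown.

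The expected effect is also small. Even at 20% switching, fewer than one PVB event is expected to land in the PEC arm. At 10%, with 1% assumed for PEC, the loss of 0.8 points is about half a patient (0.008 × 64 = 0.5). The comparison was never going to be decisive. All of this stands.

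A reader might infer that intention to treat is wrong for complications and should be confined to efficacy. The documents do not support that. Comparing complications by assignment is a valid, randomized comparison of strategies, and a second block given after a failed first one can fairly be seen as part of the assigned strategy. Counting by block received gives up randomization, and it recovers the true difference only if switching is unrelated to risk. A switch after a difficult or failed block may well be related to it.

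Finally, adverse events are recorded and followed individually, with pneumothorax and hypotension specifically tracked, so events could be reported with the block received. That is feasible, but no section commits to it.

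**Conclusion.** The gap is real but minor. The plan's only complication comparison is by assignment, while the objective and the risk lists are by procedure. If patients switch blocks, the reported difference shrinks by the factor 1 − 2c under symmetric switching. With 5% for PVB, an assumed 1% for PEC and switching unrelated to risk, 4.0 points becomes 3.6, 3.2 or 2.4 at 5%, 10% or 20% switching. With none, the assigned-arm and by-block-received results are identical.

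A reader might also infer that the trial will misattribute complications or conceal a safety difference. The documents do not support this: they give no switching rate and no PEC complication rate, and the expected number of misplaced PVB events is below one across the range examined. What they do support is adding a second table, with its rule fixed before events are known.

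**What to change.** Keep intention to treat for narcotic use and the other efficacy outcomes, and keep the complication comparison by assigned arm. Add to Section 9b that complications and adverse events will also be tabulated by block actually received, among patients who received a block. Patients given both blocks, no block, or a block other than the one assigned should be listed separately, with any events they had, so that a reader can move between the two tables.

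The denominator should be patients who received a block, not those in whom one was attempted: the listed data items record the technique used, and an abandoned attempt is not among them.

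Before events are attributed by block, reconcile the Adverse Events text of Section 10, which ties pneumothorax and hypotension to PEC, with the lists in the same section, which place them under PVB.

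The cost is one or two sentences. The block used is already a data item, and the sample size stays at 64 per arm. The downside is small: the added table is not a randomized comparison, its denominators may differ from 64, and it should be labelled accordingly.

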Patients will be referred by the Spectrum Health breast surgeons. If the patient is interested, the investigator or research staff will provide a copy of the informed consent for the patient to review. Spectrum Health research staff will then follow up with the patients to further discuss the study and confirm that the patient is interested in participation.

Patients will then be consented by a clinical research coordinator. Typically, this would occur at the hospital where they will be undergoing their surgery. The coordinator will review the consent with the patient (and family or significant other, as applicable) and have the patient sign it. The coordinator will make all reasonable attempts to keep the discussion as private as possible. In order to minimize coercion, it will be made very clear to patients that their participation is strictly voluntary and that not choosing to participate will in no way affect their present or future care at Spectrum Health.

Once the patient has been randomized to either PEC or PVB, the anesthesiologist on call for local blocks will see the patient and review that analgesic plan and the risks of that specific procedure with the patient. This meeting and explanation are standard, but they may also answer questions the patient may have related to the study.

We anticipate enrolling 128 total patients in the study, 64 in the PVB arm and 64 in the PEC arm.

There will be no payment to patients for inclusion in the study.

b. Inclusion and Exclusion Criteria

Inclusion Criteria:

- i. Female patients \geq 18 years of age
- ii. Total mastectomy or partial mastectomy with or without reconstruction OR planned lumpectomy.
- iii. Patient determined by their surgeon as medically able to receive a regional block for post-operative analgesia
- iv. Patient agrees to participate in the study and signs informed consent

Exclusion Criteria:

- i. Neoadjuvant radiation therapy
- ii. Stage IV cancer
- iii. Planned general anesthesia use during surgery
- iv. Allergies to ropivacaine, midazolam, fentanyl, or propofol
- v. Pregnant women
- vi. Prisoners
- vii. Adults unable to consent
- viii. Non-English-speaking patients

c. Study Endpoints

Primary Outcome Variables:

Intraoperative narcotic use, Post Anesthesia Care Unit (PACU) narcotic use and postoperative narcotic use. We would expect that all variables will have a lower values in patients randomized to PEC versus PVB.

Secondary Outcome Variable(s):

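### With equal analgesia as the objective, intention to treat as the only analysis set needs a supporting received-as-assigned analysis

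*Combined protocol and SAP*

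**What the plan says.** Section 4 states the primary objective as "To determine if pectoral nerve blocks (PECs) achieve equal analgesia following mastectomy, partial mastectomy or lumpectomy". The background (section 5) and the potential benefits (section 11) also present the pectoral block as offering equal efficacy with fewer complications.

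The rest of the plan is built to find a difference. The Study Endpoints subsection says "We would expect that all variables will have a lower values in patients randomized to PEC versus PVB". Section 9a defines the primary outcome as the "difference in narcotic use between the PEC group and the PVB group during the first 24 hours following surgery" and sizes the trial for an unpaired t-test. No equivalence or non-inferiority margin appears, and no confidence-interval rule.

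The analysis set is given in one sentence of section 9b: "The data will be analyzed as intention to treat". No per-protocol, as-treated or received-as-assigned analysis is mentioned.

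The plan foresees some departures. The procedures subsection allows conversion to general anesthesia when the patient cannot tolerate the operation under sedation and block, or when the surgeon prefers it: "This will not disqualify the patient, but the conversion will be noted in REDCap". Section 10 lists "Incomplete nerve block" as a risk of both techniques and puts every listed risk below 5%. Data already collected on withdrawn patients are used. There is no analysis rule for a patient who receives the other block or none. The block used and the pain-control techniques are recorded.

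**The concern.** Intention to treat is cautious when the claim is that two treatments differ, because switching shrinks the observed contrast. The same shrinkage is not cautious when the claim is that they are equal. A patient assigned one block who receives the other contributes that other block's outcome to the wrong arm, and the means move toward each other. Where a block is not delivered in either arm, part of the contrast disappears.

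At stake is the meaning of a finding of equal analgesia. It could reflect similar performance of the blocks, or it could partly reflect assigned blocks that were not given. The plan specifies no comparison that would separate the two.

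**Working it through.** **Inputs.** From section 9a: "the mean narcotic use in the PVB group is twice that seen for the PEC group"; the SD equals the paravertebral mean; alpha 0.05; beta 0.20; 64 per arm. Sidedness is not stated. Rates of switching and non-delivery are not given and are assumed below.

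**Step 1: the plan's own figure.** Let the paravertebral mean be M. The pectoral mean is M/2 and the SD is M, so d = (M − M/2)/M = 0.50. For a two-sided t-test with 64 per arm, the noncentrality is d × √(n/2) = 0.50 × √32 = 2.83 on 126 degrees of freedom. Power is 80.1%, so the stated 64 reproduces. A one-sided test would need only 50 per arm, so the calculation is a two-sided test for a difference.

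**Step 2: dilution.** If a fraction c of each arm receives the other block, and those patients have the mean outcome of the block they receive, the intention-to-treat contrast is d(1 − 2c). If a fraction f of both arms has no effective block and these patients have the same outcome in either arm, it is d(1 − f). The SD is held fixed.

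| Assumption | Contrast (SD) | Power | Chance of a non-significant result |
|---|---|---|---|
| None | 0.50 | 80.1% | 19.9% |
| c = 5% | 0.50 × 0.90 = 0.45 | 71.4% | 28.6% |
| c = 10% | 0.50 × 0.80 = 0.40 | 61.2% | 38.8% |
| f = 5% | 0.50 × 0.95 = 0.475 | 76.0% | 24.0% |
| f = 10% | 0.50 × 0.90 = 0.45 | 71.4% | 28.6% |

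The test is two-sided, so the same figures apply to a 0.50 SD difference in either direction.

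**Step 3: does a margin remove the problem?** Assume, for illustration only, a non-inferiority margin of 0.50 SD at one-sided 0.025. The standard error is √(2/64) = 0.177 SD. If the true block-to-block deficit sits at the margin, the chance of wrongly passing is Φ((0.50 − diluted contrast)/0.177 − 1.96):

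- no deviations: Φ(−1.96) = 2.5%
- c = 5%: Φ(0.05/0.177 − 1.96) = 4.7%
- c = 10%: Φ(0.10/0.177 − 1.96) = 8.2%
- f = 5%: Φ(0.025/0.177 − 1.96) = 3.5%

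A margin is necessary for an equality claim, but it does not undo dilution.

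**Step 4: failed blocks behave differently.** Suppose the blocks perform identically when they work, and failures occur in one arm only and raise narcotic use by an assumed 1 SD. The intention-to-treat difference is then f × 1 SD, which is 0.05 SD at 5% and 0.10 SD at 10%. The arms move apart, and that difference is real. Removing the failures would hide it.

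**The case against.** The strongest reply is that the planned test is for a difference, for which intention to treat is the usual primary set, and dilution works against a positive finding. Dilution favors equality only if a non-significant t-test is read as equality, and that fault lies in the mismatch between objective and test. This stands in large part: a further analysis set alone would not make equality demonstrable. It does not dispose of the point, because the stated objective is equality and step 3 shows that dilution persists once a margin is supplied.

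A second reply is that switching may be rare. Patients who will not accept either allocation are not enrolled, the coordinator tells anesthesia which block was assigned, and randomization and the block fall on the day of surgery. The only related figure is the ceiling of under 5% for incomplete block. At 5%, alike in both arms, the miss rate is 24% against 20%. That is fair as to size, although the ceiling does not cover switching or surgeon-preferred conversion.

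A reader might infer that every deviation, including failed blocks and conversions, makes the arms look alike. The documents do not support this. Conversion can follow from inability to tolerate surgery under the block, which is a result of the treatment, and step 4 shows that unequal failure separates the arms. For the same reason, a per-protocol set that drops conversions and second blocks could conceal a real difference.

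A reader might also infer that deviations would go unseen. Block used and conversion are recorded, and the planned percentages and chi-square tests could tabulate them by arm. The plan does not say that they will.

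**Conclusion.** The point holds in limited form. With equality as the objective and intention to treat as the only set, switched or undelivered blocks make an equality reading easier to reach. At assumed switching of 5% or 10% in each arm, the chance of missing the plan's 0.50 SD difference is 29% or 39%, against 20% with none. These figures rest on symmetric switching, outcomes that follow the block received, and an unchanged SD. The documents supply no rate, so the actual size is unknown and may be small. Nothing here makes intention to treat the wrong main analysis, and if the aim is superiority it suffices alone. The change is worth making because it uses recorded data and bears directly on the stated objective.

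**What to change.** In section 9b:

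- Keep intention to treat as the main analysis.
- Pre-specify a supporting analysis of first-24-hour narcotic use in patients who received the block they were assigned.
- Do not exclude incomplete blocks, supplemental blocks given for failure, or conversions to general anesthesia. Report these by arm, and show conversions for surgeon preference separately where the reason is known.
- Report both analyses as differences with confidence intervals.
- If equality stays as the objective, conclude it only when both intervals meet the same pre-stated equivalence or non-inferiority criterion, never from a non-significant t-test.
- If superiority is the aim, reword the objective in section 4; intention to treat alone is then acceptable.

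**Cost.** SAP wording and one repeat of an existing analysis. Block received and conversion are already captured. The received-as-assigned set is smaller: losing an assumed 10% leaves about 64 × 0.90 ≈ 58 per arm and widens the interval by about 5% (√(1/0.90) = 1.05). It is not fully protected by randomization, so it supports intention to treat and does not replace it. Requiring both intervals to pass makes equality somewhat harder to claim.

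The choice of criterion has its own sample-size consequence. By n = 2((1.96 + 0.84)/margin)² per arm, for non-inferiority with no true difference, 80% power and one-sided 0.025, an assumed margin of 0.50 SD needs 63 per arm, 0.40 SD needs 99 and 0.25 SD needs 252.
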